5.2.7 Risk level assignment modification in risk-based arm

These risk-based screening recommendations might be subject to evolution during the trial, both at a personal participant level and at a general trial level

- At a personal level, a web-based yearly update will be organized for all women in the risk-based arm to better adapt their risk profile if required (only if change of family history, if personal benign breast biopsy, if identification of atypical lesions or if identification of a germline high risk mutation; as described before). See section 5.5
- At the trial level, the re-evaluation will take into account published evidence-based knowledge notably based on SNPs

Other measures associated with risk level:

GERMLINE GENETIC TESTING

Of note, for the women identified as having a high-risk family-history, genetic counselling might be advised, according to national and international guidelines. This advice will be part of the recommendations produced by the risk assessment tool. This genetic counselling will be performed in the standard genetic network of the country, and genetic testing for the search of germline BRCA1/2 mutations (or panel testing) usually performed in a cancer-affected relative rather than in the healthy consultant. Such women will of course remain within the trial, and be assigned high or very high-risk categories, with the adequate proposed follow-up.

In Israel specifically, it has been planned that women who have signed a dedicated informed consent (proposed to all participants at trial entry) will have an additional evaluation of polymorphisms together with their SNP score, aiming at identifying the presence of one of the three Ashkenazi founder mutations. Such finding will prompt genetic testing for confirmation, as described previously.

BREAST CANCER RISK REDUCTION MEASURES

Participating women will receive standardized self-awareness recommendations, although they will remain free to comply with them. They will be informed on potential risk-reducing strategies associated with their individual breast cancer risk level and individual risk factors. Upon risk calculation, they will receive a printed + online document summarizing all their personal information, risk category assignment, proposed screening strategy, but also suggested personalized risk-reduction measures (such as avoidance of certain endocrine therapies, dietary and exercise recommendations, etc...). These measures have been predefined by the trial steering committee.

Participants will be able to retrieve all their personal information from their personal account on the trial's web platform. They also will be able to gather more general information on the project's website

5.3 Imaging protocols and techniques used in both arms

It is crucial that imaging quality is high in the present study. Monitoring of the imaging quality and dose administered will be implemented through continuous data collection and audits will be conducted.

The participation screening centres will be asked to adhere a simple quality chart derived from ASSURE and European guidelines (ECIBC), derived from/in line with the previous experience of several members of the consortium in such projects as ASSURE and in the construction of European QA guidelines (ECIBC). This QA chart will indeed be inspired by ECIBC guidelines platform for all breast cancer processes and quality assessments

(<http://ecibc.jrc.ec.europa.eu/-/the-ecibc-guidelines-platform-for-all-breast-care-processes>
<http://ecibc.jrc.ec.europa.eu/documents/20181/22500/EC+Initiative+on+Breast+Cancer.pdf/a586dfb5-83d2-4ee3-a345-9ddf72363fa8>).

Radiologists will be asked follow the best standard procedures and the on-going national and European recommendations regarding all imaging procedures throughout the study, whatever the arm participants are randomized to.

5.4 Women's discontinuations of assessment/follow-up

Women can discontinue the study MyPeBS for the following reasons:

- End of study: all women will discontinue from the study and go back to routine screening at 4 years from randomization
- Women decline further assessment but accept to continue with answering questionnaires
- Personal reasons such as moving to an area where the study is not available
- Investigator's decision
- Death

Women who discontinue assessment/follow-up will continue with the study and the protocol-defined procedures, unless they specifically withdraw their consent and indicate that they do not want to perform any further study-related visits or assessments (for woman withdrawals see Section 5.).

5.5 Change of ongoing schedule

Women in the following conditions will remain on study unless they do not wish to, but their schedule might be altered/modified:

- Women who are diagnosed a benign lesion and had to undergo a mammographic control
 - o The participant's schedule may be reorganised to fit with the new schedule of mammograms. Risk must be reassessed with this new information
- Women who are diagnosed with an atypical breast lesion or in situ carcinoma of the breast.
 - o The participant's schedule may as well be reorganised to fit with the new schedule of mammograms. Risk must be reassessed with this new information
- Women who are diagnosed an invasive breast adenocarcinoma or another breast cancer during the trial
 - o They can remain on trial but their risk will be reclassified as high risk and their further schedule adapted accordingly
- Women who had their risk recalculated based on other personal or familial events which have changed their risk level
 - o A new schedule will be provided upon risk recalculation
- Pregnant women
 - o A new schedule will be provided based on participant's availability
- Women who require a modification in their schedule for the advent of a medical condition that is no longer compatible with the scheduled examinations
 - o Women will remain on trial and their schedule adapted accordingly
- Women who require a modification in their schedule for other personal reasons
 - o This must absolutely be limited but may be punctually acceptable

6. EVALUATION OF EFFICACY

6.1 Efficacy evaluation

The primary evaluation endpoint is the incidence rate of stage 2 + breast carcinoma after 4-years of follow-up from the randomization.

6.2 Safety evaluation

6.2.1 Specific screening-linked safety

In this trial, safety assessments concern some of the secondary endpoints which measure parameters considered as "safety evaluations" since they are linked to screening-related harms:

1. False positive recalls have been defined in the end points and will be carefully scrutinized
2. Overdiagnosis will be estimated
3. The theoretical radiation exposure and potential associated radiation-induced cancer risk will be estimated

6.2.2 **Classical safety:**

Beside these specific screening-linked safety evaluations, no other safety evaluations linked to daily assessments and imaging are planned: as the present clinical trial is totally based on current practices, there is no obligation for any specific AE reporting within MyPeBS.

However, we will take some risk reduction measures for this trial:

- **Breast cancer risk reduction measures in the standard arm**

Participants in the standard arm will be informed on potential risk-reducing strategies. They will be provided written and on-line information material and encouraged on these predefined measures.

Participants will be taught breast self-palpation if they wish so, but this will not be mandatory within the trial.

- **Germline genetic testing**

Of note, for the women identified as having a high family-history, genetic counselling will be advised, according to national and international guidelines. This advice will be part of the recommendations produced by the risk assessment tool. This genetic counselling will be performed in the standard genetic network of the country, and genetic testing for the search of germline BRCA1/2 mutations (or panel testing) usually performed in a cancer-affected relative rather than in the healthy consultant. Such women will of course remain within the trial, and be assigned high or very high risk categories, with the adequate proposed follow-up.

Specifically in Israel, women who have signed a dedicated informed consent will have an additional evaluation of polymorphisms together with their SNP score, aiming at identifying the presence of one of the three Ashkenazi founder mutations. Such finding will prompt genetic testing for confirmation, as described previously.

- **Breast cancer risk reduction measures in risk-based arm**

Participants will be informed on potential risk-reducing strategies associated with their individual breast cancer risk level and individual risk factors. Upon risk calculation, they will receive a printed + online document summarizing all their personal information, risk category assignment, proposed screening strategy, but also suggested personalized risk-reduction measures (such as avoidance of certain endocrine therapies, dietary and exercise recommendations, etc). These measures have been predefined by the trial steering committee.

Participants will be able to retrieve all their personal information in their personal account on the trial's web platform. They also will be able to gather more general information on the project's website.

7. DESCRIPTION OF VISITS AND INVESTIGATIONS

In this trial, organized Breast screening structures (OBSS) will be involved to coordinate women's information on the trial and data retrieval.

The nature of recruiting centers will be different depending on the country: in most countries, centralized screening centers will be the recruiting centers, whereas in France, recruiting centers will be a defined list of community GPs, Radiologists and gynecologists in participating areas.

In all countries, coordination centers will centralize data retrieval and pseudonymization for transmission to the database. The number of coordinating centers will vary country by country (3 in Belgium, 3 in UK, 4-6 in Italy, 11 in Israel, 40 in France).

7.1 Clinical centers

To select the participating sites, we will have different approaches according the strategy of the screening organization of each country.

In UK, Italy, Israel and Belgium, the screening program is organized with limited centralized screening centers and we have already identified them and obtained the involvement for most of them (3 for Belgium, 4-6 regions for Italy, 2-3 areas in UK and 11 centers for Israel). They will be the recruiting centers.

In France, the process of site selection is different. The recruiting centers will be either community of general practitioners, radiologists and gynecologists in the 15 participating areas.

- Women aged from 40 to 70 years will be informed of MyPeBS trial by the screening structures of their area
- They will be included by one of the participating physician in the area (either a GP, or radiologist, or gynecologist)
- Data collection of exams and follow-up will be coordinated by the screening structures

For further information, see the appendix

7.2 Information of potential participants

In each country (but only in the area participating in this trial), women of general population aged 40-70 years old will be informed of MyPeBS trial by the coordinating physician of their regional national screening program. In the framework of this trial, public web-platform containing information about this trial and the patient informed consent will be available to inform women in parallel of this personal information.

7.3 Baseline visit (V0)

Women eligible for the study and having signed the informed consent form will perform a baseline visit. Women can be provided with the informed consent sheet and have a 2 weeks reflection time potential interval before trial accrual.

Upon signature of the informed consent, women can be immediately randomized either in standard screening arm or in risk-based arm.

During this visit, the investigator has to create the profile of the woman into the web-platform and to interview the woman for retrieving medical history and medical data.

Women have to answer the following questionnaires (via a touchpad, a phone or via their own profile on web-platform):

- Socio-demographic and economical status questionnaire
- Comprehension questionnaire
- State anxiety
- Quality of life (EQ-D)

After written informed consent has been obtained, the study site will obtain a unique patient number or unique patient identifier which will stay the same throughout the entire study covering all study periods (as described in section 12). At this time point the patient is enrolled into the study.

Women who have signed the informed consent and fulfill all eligibility criteria will be randomized directly online by the investigator, 1:1 to either standard-of-care screening or a risk-based screening strategy.

Women will be randomized for either arm immediately during the accrual visit through the use of the online real-time randomization module of the trial.

The results of the randomization will be immediately provided. See study scheme.

- Women randomized to the standard arm will immediately receive their personal "standard" screening schedule for the next 4 years. No other visit with the investigator is formally planned.
- Women randomized to the risk-based arm will be asked to provide a saliva sample. Their breast density will be evaluated. They will be scheduled for a second visit (physical or by telephone interview according to national/local regulations), during which they will be communicated their risk estimation and their personalized, risk-based, screening schedule/plan for the next 4 years. The saliva sample will be sent to the central lab for DNA extractions and genotyping.

7.4 Visit 1 or phone call (more and less 8 - 12 weeks after the randomization date - V0) only for women randomized in risk-based screening program

These women will come back for a second dedicated visit (physical visit in France and Belgium) or be reached by their investigator through a dedicated phone call (for the other countries) to inform them regarding their personal risk evaluation result and proposed screening program.

The investigator has to record the score result into the website and to give the woman her schedule screening program personalized on her risk. The risk results will be communicated orally as well as through written documents available on the participant's personal portal.

The women's follow-up schedule will be organized from that time (automatic planning based on previous mammogram)

7.5 Imaging examinations (follow-up during 4 years from randomization)

Women have to perform imaging exams according the scheduled screening program given to her. All women must perform a final imaging exam at the end of the 4-years follow-up.

7.6 End of study visit and mammogram

- No end of study visit will be performed.
- Women will follow their current screening schedule until 4 years from randomization
- Women in the risk-based arm who were evaluated at low risk and did not get mammogram during 4 years, will have an end of study mammogram (specific invitation)
- After 4 years, the women' later screening schedule outside of study will be determined with her usual treating physician

7.7 Update of participants' data on the web-platform

During the trial, there will be different levels of data updates on the web-platform:

- **direct updates by woman:** they will be required to update yearly on their personal portal the date and type of imaging exams potentially performed according to their own screening program; the questionnaires at months 3, 12, and 48 (for more details for the questionnaires, please refer to schedule of activities page 13-14 and appendix 04). Women will be asked to report all relevant new data that might affect risk evaluation or screening schedule
- **updates from the organized breast screening structures and/or investigators according to countries:** results of screening examinations or events
- **cross-over with database of national insurance system** at the end of the study (at the end of the study).

7.8 Provisions in case of assessment or study interruption

If the study assessment is discontinued by a woman, further follow-up and assessment will be at the investigator's discretion as per screening standard. If the woman developed a breast cancer, she will take care as usual practice by her general practitioner, who will address her to a specialized center.

7.9 Participation of women in other clinical trials

Participants in MyPeBS can eventually participate in other clinical trials, whatever the field. It is however asked that they inform their investigator if they consider such participation, who in turn will ask the sponsor. The sponsor will check whether the safety of the participant and the integrity of MyPeBS trial is preserved, in case of such participation.

The sponsor may ask the woman not to participate to another trial in specific situations where both participants safety and trial's integrity cannot be preserved. Alternatively, the woman may discontinue her participation in MyPeBS.

8. DESCRIPTION OF STATISTICAL METHODS

An initial statistical analysis plan (SAP) will be produced by the statistician before the inclusion of the first woman (version n°1). This document will be validated by the Steering Committee. The SAP may be revised during the course of the study in case of substantial modification of the protocol or following recommendations of the Independent Data Monitoring Committee. Any revision of the SAP will be validated by the Steering Committee.

8.1 Statistical hypothesis and sample size determination

Randomization

Women who have signed the informed consent will be assigned a unique participant identifier and will be randomized 1:1 to either standard screening or the risk-based screening strategy. Randomization will be performed through an automated real-time online system (permutation blocks).

Stratification

Randomization will be stratified by country, age (women aged <50 vs ≥ 50), and prior mammogram (yes or no). This will ensure to balance screening modalities, global population risks, and the rate of prevalent breast cancers at entry.

Required number of women to be included

The incidence rate of stage 2 + breast cancer in the MyPeBS standard arm is expected to be around 120 cases/100,000/year. This number is derived from what is observed in the screened populations of European countries and including women aged 40 to 50 years for whom the incidence rate is lower:

- Incidence in women aged 50-74 years old is 140 cases/100,000 women/year on average in screened populations taking into account interval cancers and cancers not detected in women who are not screened
- We expect to include 25% of women aged between 40-49 years old
- Incidence in women aged 40-49 years old is half than older women
- Expected incidence of stage 2+ breast cancers for 100,000 women followed up for 1-year in the standard arm of MyPeBS is therefore: $(140 \times 0.75) + (0.25 \times 0.5 \times 140) = 105 + 17.5 = 122$. A slightly conservative estimate is therefore 120.

We anticipate a drop-out rate lower than 5% in both arms, and non-compliance rates of 10% in the risk-based screening arm and of 30% in the standard arm. These women will not be included in the per-protocol analysis due to non-compliance, in the 4-year period after inclusion.

The primary hypothesis is that the risk-based screening arm will be non-inferior to the standard screening arm in terms of cumulative hazard rate in the per-protocol population. The cumulative hazard functions of cancers of stage 2 + will be compared between the 2 study arms.

Further assumptions are a non-inferiority margin of a 25% relative increase in the risk-based arm (null hypothesis $H_0: \lambda_e/\lambda_c \geq 1.25$ with t and c standing for experimental and standard arm, respectively; it corresponds to an absolute increase in the cumulative hazard rate of stage 2 cancer or higher after 4 years up to 120/100000 stage 2 cancers the risk-based arm under H_0), 80% power, 2.5% significance level, 1-sided test. If we assume that under the alternative hypothesis a 10% relative improvement can be expected by the experimental risk-based-stratified screening arm (i.e. $\lambda_e/\lambda_c = 0.9$) due to our anticipated increase in the average numbers of mammograms in the experimental arm, a total of 298 stage 2 breast cancers are required for the non-inferiority assessment using a logrank test. We assume a total of 85,000 participants, 42,500 in each arm, to be included over 2.5 years.

For the primary and key secondary endpoint analysis, each subject will be followed for four years, to be able to compare cycles of mammograms between the 2 screening arms. Later updates of the trial analyses will be performed using longer follow-up.

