Apart from very rare patients at very high-risk, age is currently the only criterion for starting screening. Depending on the country, mammograms are offered every 1 to 3 years, starting from the age of 40-50 years up to 69-74 years.

These screening recommendations are based on large-scale randomized studies (New York, Malmo 1 and 2, Edinburgh, Swedish 2 county, Canada trials 1 and 2, Stockholm, Goteborg, UK age trial) that have globally shown that screening reduced breast cancer specific mortality by about 20% in the intent-to-treat populations (invited women), or 30-40% in the per-protocol populations (participating women).

Several reappraisals of these mammographic screening-associated benefits in the randomized trials have been published in the past 10 years with variable interpretation of data. Indeed, trials' methodologies are somehow heterogeneous most trials dated at times incidence and therapies were quite different. The UK independent panel estimated the benefit of mammographic screening starting at age 50 to be in the range of one breast cancer death prevented for 250 women invited (Marmot et al, 2011).

The benefit and risk-benefit ratio of mammographic screening between the age of 40 and 50 is controversial and each country currently has its own policy. Mammographic screening has also been demonstrated to reduce the number of stage 2 and higher cancers at diagnosis in women older than 50.

Current breast cancer screening by mammography: harms and weaknesses

8,18,87,97,107,127,161,125,128,109,136,161

Current screening by mammography is associated with a number of harms or weaknesses that have been largely debated in the medical literature in the past 10 years:

1. The sensitivity of 2-yearly and furthermore 3-yearly mammogram is not optimal: 1-2 (or more for UK) breast cancers every 1,000 examined women are interval cancers (Blanch, Mandelson, Houssaimi 2017). This turns to 16 to 35% of cancers being interval cancers according to the screening interval. Furthermore, about one fourth of the cancers occurring in regularly screened women are still diagnosed at stage 2 or more.

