1.2.2.1 Potential benefits

As previously demonstrated, increased mammographic screening intensity (up to yearly mammogram) has been clearly demonstrated as to increase screening sensitivity. It is currently used in high-risk situations, such in women previously treated for breast cancer, atypical lesions, or previous chest wall irradiation, as well as high risk genetic conditions, together with MRI. Such MRIs have been demonstrated as highly efficient for reducing the risk of advanced breast cancer among high-risk individuals.

Decrease in the incidence of advanced breast cancers

We expect a decrease in the incidence of stage 2 and higher breast cancers, which will concern women identified at average risk and aged 40-50, or at high-risk.

According to our assumptions (Table below - based on “no screening” before 50 and mammogram every 2 years), among 530 women overall expected to develop breast cancer at 4 years in one arm (among 42,500 participants), a risk-based strategy will increase the screening intensity in 329 of the women who are expected to develop breast cancer (light green).

We should therefore avoid 50 stages 2 or higher breast cancers in women who will get more screening than they would have in the standard arm.

MyPeBS		women aged 40-49 (25%)		women aged 50-59 (45%)		women aged 60+ (30%)	
risk level	average risk in level	Expected distribution	Expected cancers at 4y	Expected distribution	Expected cancers at 4y	Expected distribution	Expected cancers at 4y
Low	0,8%	60%	41	28%	34	15%	12
Average	1.4%	25%	30	33%	71	30%	43
High	2.3%	15%	29	40%	141	55%	129
TOTAL		10 625	100	19 125	246	12 750	184

Decrease of the incidence of false positive recalls and overdiagnosis among women classified as low-risk

In women identified as having a low risk, we expect to reduce the risk of false positives findings (around 300), as well as overdiagnosis (around 5), together with the levels of the stress/anxiety induced by regular mammograms. No impact is expected on radio-induced cancers in such short term but this theoretical benefit exists.

Decrease in breast cancer risk through risk reduction measures in women identified at high-risk

Although this will not be a directly measurable effect, we can expect that women identified at high risk will consider risk-reduction measures, which may contribute in a long-term breast cancer risk reduction.

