8.2 Planned statistical analysis

8.2.1 Statistical analysis plan

A statistical analysis plan (SAP) describing in detail all statistical analyses performed will be elaborated. An intermediate progress report will be made after 1 year of inclusion to evaluate the robustness of the study with regards to estimated initial inclusion rates, expected age categories, risk predictions, and compliance to screening recommendations, on the overall population and at the country level to recommend potential changes to the protocol and/or study management. Indeed if the age and risk structure of the population appeared significantly different from those expected, with potential important influence on the study's power or ability to conclude, amendments may be proposed by the Clinical Trial Steering Committee, upon advice of the Ethics and data Monitoring Committee.

This progress report will be updated after 2 years of inclusion and during the follow-up period after the last woman randomization.

Beside this, the spread of SNPs chosen and harmonious population repartition will be verified after 5,000 women are included.

All the analyses for the progress reports will be conducted blinded from the efficacy outcomes of the study (breast cancer incidence). Once all the participants have been followed for 4 years, the cleaned database will be locked and a final statistical report prepared.

The primary analysis will compare the cumulative hazard functions of cancers of stage 2 + between the two randomized groups of women using a logrank test. The rate of cancers of stage 2 + cancers for each arm will be estimated as the number of cancers of stage 2 + detected either clinically or by screening out of the total person-years of follow-up.

The primary non-inferiority analysis will be performed on the per-protocol (PP) population, which will include all randomized and eligible women in the arm they were randomized to, who complied with their screening recommendation in terms of number of mammograms. The analyses will be repeated in the Intention-To-Treat (ITT) population for sensitivity. An additional sensitivity analysis, we will be performed using causal inference methods to estimate the average effect of the risk-based screening versus standard screening on stage 2 incidence as if all participants will have complied with the protocol.

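### The 80% power applies a stage 2+ rate that counts cancers in unscreened women to a primary set that keeps only compliers, so power in that set is probably below 80%

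*Protocol*

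**What the plan says.** Section 8.1 takes 140 per 100,000 per year at ages 50-74, "on average in screened populations taking into account interval cancers and cancers not detected in women who are not screened". It halves this for ages 40-49, weights 75:25 to 122.5 (the figure in the synopsis), and rounds to 120. It expects drop-out below 5% in each arm, and non-compliance of 10% in the risk-based arm and 30% in the standard arm, and adds: "These women will not be included in the per-protocol analysis due to non-compliance".

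The design is "80% power, 2.5% significance level, 1-sided test", with "a non-inferiority margin of a 25% relative increase in the risk-based arm". Under the alternative, "a 10% relative improvement can be expected by the experimental risk-based-stratified screening arm". This leads to 298 required events from 42,500 women per arm, each followed for 4 years. Section 8.2.2 runs the final analysis when all women remaining on study have reached 4 years; no event count triggers it.

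Sections 8.2.1 and 8.3.1 define the per-protocol set by number of mammograms. A standard-arm woman aged 50-70 with no mammogram is excluded. A standard-arm woman in her forties for whom no mammogram is planned is compliant if she has at most one.

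Two other places bear on the rate. Section 1.1.2 says that "about one fourth of the cancers occurring in regularly screened women are still diagnosed at stage 2 or more". Section 1.2.2.1 works from a projection "among 530 women overall expected to develop breast cancer at 4 years in one arm (among 42,500 participants").

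**The concern.** The rate and the analysis set describe different women. From age 50, the 140 counts cancers in women who are not screened, while the primary set removes standard-arm women who had no mammogram. The protocol itself reports that screening lowers the risk of higher-stage cancer from age 50 (section 1.2.1: relative risk 0.62, 95% CI 0.46 to 0.83). Compliers should therefore have a rate below 140.

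If so, the primary analysis will hold fewer than 298 events, and a strategy that meets the design's own alternative will fail to show non-inferiority more often than the planned one time in five. The superiority test would be lost with it, because it is reached only after non-inferiority.

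**Working it through.** **Inputs.** One-sided alpha 0.025, margin 1.25, true hazard ratio (HR) 0.90, 42,500 women per arm, 4 years, drop-out 0-5%, compliers 70% standard and 90% risk-based (all section 8.1). Relative risk 0.62 (section 1.2.1). Cancers over 4 years per arm: 100 in 10,625 women aged 40-49 and 246 + 184 = 430 in 31,875 aged 50+ (section 1.2.2.1). One-fourth share (section 1.1.2).

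**Formulas.** Required events = 4 × (1.96 + 0.84)² / [ln(0.90/1.25)]². Expected per-protocol events D = 42,500 × (1 − drop-out) × 4 × rate × (0.70 + 0.90 × 0.90). Power = Φ(½ × √D × ln(1.25/0.90) − 1.96).

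**Step 1: the plan's own figures.**
- Required events: 291 by Schoenfeld with 1:1 allocation, 296 with the per-protocol allocation of 0.7/1.6, 297 by Freedman. The stated 298 is sound.
- Expected at 120 per 100,000: 293 with 5% drop-out (power 80%), 308 with none (82%).
- Expected at 120 with 5% drop-out but no non-compliance exclusion: 42,500 × 0.95 × 4 × 0.0012 × 1.9 = 368.

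So the size of the trial fits 298 only if 120 is applied to compliers, and there is almost no reserve.

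**Step 2, route A: take unscreened women out of the 140.** Let p be participation in the population behind the 140, which the protocol does not give. The screened rate at 50+ is 140 × 0.62 / (0.62p + 1 − p). Ages 40-49 stay at 70, because unscreened standard-arm women of that age are mostly per-protocol by definition. Overall rate = 0.75 × screened rate + 17.5. With 5% drop-out:

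| Assumed p | Rate at 50+ | Overall rate | Per-protocol events | Power |
|---|---|---|---|---|
| 70% | 118 | 106 | 259 | 75% |
| 50% | 107 | 98 | 239 | 72% |
| 30% | 98 | 91 | 222 | 69% |

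The 70% mirrors the 30% standard-arm non-compliance; section 1.1.2 reports participation of 25-30% in some regions. Over the interval 0.46 to 0.83 for the relative risk, power at 70% participation runs from 71% to 79%.

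**Step 3, route B: apply the one-fourth share to the projected cancers.**
- All cancers at 50+: 430 / (31,875 × 4) = 337 per 100,000 per year. One fourth is 84.
- All cancers at 40-49: 100 / (10,625 × 4) = 235. The stage 2+ share is not given; 25-45% is assumed.
- Overall rate: 0.75 × 84.3 + 0.25 × 235 × (0.25 to 0.45) = 78 to 90.
- With 5% drop-out: 190 to 219 events, power 62% to 68%.

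**Step 4: do the three sections agree?** A rate of 120 over 42,500 × 4 = 170,000 person-years is 204 stage 2+ cancers, or 204/530 = 38% of those projected. At 50+, 140 gives 178.5 of 430, or 42%. Neither matches one fourth.

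**The case against.** Several points on the other side stand, in whole or in part.

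- **The sample-size arithmetic is correct.** A reader might infer a calculation error. There is none: 298 reproduces. The problem is the rate fed into it.
- **62-68% is not the single result of the protocol's figures.** It is tempting to read it that way, but it multiplies a background statement whose base is undefined by a risk-model projection of invasive cancers. Removing unscreened women from the 140, which is the actual mismatch, gives 69-75% under the assumed participation.
- **Per-protocol is not the same as regularly screened.** Section 8.3.1 accepts a single mammogram in 4 years at ages 50-70. It also excludes over-screened women: four or more mammograms at 50-70, or two or more in the forties where none is planned. The 30% is therefore not simply the unscreened share, and removing over-screened women could raise the per-protocol rate.
- **The protocol's benefit projection is more favourable than HR 0.90.** Sections 1.2.2.1 and 1.2.3 expect 50 stage 2+ cancers avoided against a pessimistic excess of 5. A net 45 of 204 is a 22% reduction (HR about 0.78). Even at 78-90 per 100,000 this would give about 176-203 per-protocol events and power of 88-92%. But section 8.1 states its power at 0.90; a larger true effect does not support that statement.
- **A shortfall need not stay hidden.** Because the progress reports are restricted ("All the analyses for the progress reports will be conducted blinded from the efficacy outcomes of the study (breast cancer incidence"), a reader might infer that nothing would reveal it before the end. Section 12.4 contradicts this: minutes of the EDMC, which meets at least yearly, give the number, frequency and stage of cancers in the whole included population. Section 9.2 lets that committee request analyses and recommend more events or participants. What is missing is a link from those counts to the 298 or to any projection.

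**Conclusion.** The concern holds in a limited form. The 120 rests on a rate at ages 50-74 that includes unscreened women's cancers, yet it is applied to a primary set without non-compliers. Expected per-protocol events of 293-308 only just meet 298 and the analysis is fixed by time, so the stated 80% is not supported for the set analysed.

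The size is uncertain. With HR 0.90 held and 5% drop-out, power is about 69-75% by route A and 62-68% by route B. Route A rests on the relative risk of 0.62 and an assumed participation of 30-70%; route B rests on the one-fourth share and an assumed 25-45% at ages 40-49. The mismatch mainly concerns women aged 50 and over. Separately, sections 1.1.2, 1.2.2.1 and 8.1 do not agree on the share of cancers at stage 2 or higher.

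**What to change.** In section 8.1, reconcile the 140, the one-fourth share and the projected 530 cancers. State a stage 2+ rate specific to the per-protocol set as section 8.3.1 defines it, by age group, and say what participation lies behind the 140. Give the expected per-protocol events beside 298, with the resulting power as a range.

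Have the pooled, arm-blind stage 2+ count that the EDMC already receives each year compared with that projection, so that analysis timing can be decided before database lock. Four-year compliance is not complete until the end, so the projection should also be given for all randomized women.

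The cost is a less favourable stated power and one pooled comparison. No unblinding is needed.
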